**Intervention Groups and Duration:**

The following study interventions will be administered in the study:

- Osocimab (BAY 1213790): sponsor's study drug under investigation
- Placebo to osocimab

Different doses will be achieved by administering a different volume.

- Low dose cohort  
105 mg single loading dose as subcutaneous abdominal injection at visit 5, followed by monthly (i.e. 30 days  $\pm$  3 days) maintenance doses of 52.5 mg starting at visit 8 until the end of the extension treatment period. Placebo will be administered subcutaneously in the same manner as osocimab.
- High dose cohort:  
210 mg single loading dose as subcutaneous abdominal injection at visit 5, followed by monthly (i.e. 30 days  $\pm$  3 days) maintenance doses of 105 mg starting at visit 8 until the end of the extension treatment period. Placebo will be administered subcutaneously in the same manner as osocimab.

The two dose cohorts (low dose and high dose) follow the same treatment schedule:

- **Screening period (visit 1):** up to 14 days
- **Randomization (visit 2):** 1 day
- **Pre-treatment period (from visit 2 until visit 4):** 7 days
- **Main treatment period (from visit 5 until EOMT visit):** 6 months
- **Extension treatment period (from visit 19 until EOET visit):** up to 12 months
- **Follow-up period (from visit 32 until visit 35):** 4 months after end of treatment (EOMT or EOET)

The mandatory extension treatment period is continued until the last study participant has completed its 6 months main treatment period or to a maximum of 18 months (i.e. 6 months main treatment period + 12 months extension treatment period). When the last participant has completed its 6 months main treatment period including EOMT (end of main treatment period) visit, all participants who are in extension treatment period at this time point will not receive any further dosing and will participate in an EOET (end of extension treatment period) visit at the next regular monthly extension visit and will move to the follow-up period. The last participant of the whole study will not take part in the extension treatment period.

[figure not shown]
**Data Monitoring Committee:** Yes

The study will be overseen by a Steering Committee (SC), a Data Monitoring Committee (DMC) and a Central Independent Adjudication Committee (CIAC).

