## 1.2 Schema

Figure 1–1: Study Design Overview

Abbreviations: EOET = end of extension treatment period, EOMT = end of main treatment period, LD = loading dose, MD = maintenance/ monthly dose, pts = participants, R = randomization, V = visit

Further details on the randomization schema can be found in Section 6.3. The follow-up period ends 5 months after last study intervention and 4 months after EOMT or EOET.

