### 6.1 Study Interventions Administered

The following study interventions will be administered in the study:

- Osocimab (BAY 1213790): sponsor's study drug under investigation
- Placebo to osocimab

Different doses will be achieved by administering a different volume:

- Low dose cohort

105 mg single loading dose as subcutaneous abdominal injection at visit 5, followed by monthly (i.e. 30 days  $\pm$  3 days) maintenance doses of 52.5 mg starting at visit 8 until the end of the extension treatment period. Placebo will be administered subcutaneously in the same manner as osocimab.

- High dose cohort:

210 mg single loading dose as subcutaneous abdominal injection at visit 5, followed by monthly (i.e. 30 days  $\pm$  3 days) maintenance doses of 105 mg starting at visit 8 until the end of the extension treatment period. Placebo will be administered subcutaneously in the same manner as osocimab.

Participants will be treated up to 18 months.

Osocimab/ placebo is administered within one hour (60 minutes) prior to start of dialysis session by site personnel at site.

Further details for study interventions are described in [Table 6–1](#).

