4.5 Data Rules

The pre-treatment period serves as baseline period and takes place before first study intervention was given. If there is more than one measurement, the mean of the respective measures will serve as baseline.

Baseline for PD will be visit 5 data prior to dosing.

The primary analysis will be based on all respective events that occurred during the scheduled main treatment period.

Additional analyses may be based on all respective events that occurred during the overall study period, consisting of both the main treatment and extension treatment period.

In addition, further analyses may be based on all events occurring during the full study period consisting of the main treatment, extension treatment and post-treatment follow-up period.

These time scopes are summarized in the table below.

An event is considered treatment emergent if it occurred between start of treatment and not later than 30 days after last administration of study intervention.

An event is considered as full study treatment emergent if it occurred between first study intervention and not later than 5 months after last administration of study intervention.

Additional analysis may be performed post-hoc.

Time scope definition:

Overall study period	Main treatment phase + extension treatment phase
Full study period	Main treatment phase, extension treatment phase + follow up

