6.4.5 Adverse events

The investigator has to record on the respective CRF pages all adverse events (AEs) occurring in the period between the signing of the informed consent and the end of the post-treatment follow-up period.

The original terms used by investigators to report AEs via the CRFs will be coded using the Medical Dictionary for Regulatory Activities (MedDRA). All reported adverse events during the main treatment period will be summarized by means of AE tables based on the treatment-emergent approach (see section 4.5).

All AE/SAE/AESI tables will also be provided for the following timeframe named “Full study TE AEs (SAE/AESI)”: AEs occurred after first intake of study intervention up to 5 months after last intake.

If an AESI will be reported, this will always be done separated for the two categories listed below.

For each AE, the number and percentage of subjects who experienced at least 1 occurrence of the given event will be tabulated according to the affected primary system organ class (SOC) and preferred term (PT) by treatment arm. A total column will be included in all safety summaries.

Frequency tables, showing an overall summary of number of subjects with AEs, serious adverse events (SAEs) and adverse events of special interest (AESIs) separated by the two categories will be given, and will include the following information.

- if the AE (/ SAE/AESI) occurred with causal relationship to study drug ,
- if the AE (/SAE/AESI) occurred with causal relationship to study procedures
- reasonable causal relationship to ESRD
- reasonable causal relationship to hemodialysis procedure
- maximum intensity for any AE
- maximum intensity for any study-drug related AE,
- AE related deaths.
- AE resulting in permanent discontinuation of study drug

The two categories of AESI are:

- Decrease in platelets below $75 \times 10^9/L$ or $> 50\%$ decrease in platelet count from baseline
- Hypersensitivity (i.e. any allergic reactions of \geq CTCAE criteria 2 [Common Terminology Criteria for Adverse Events] or anaphylaxis)

A similar table showing overall summary information of AEs (/SAE/AESI) during screening will be given.

Additionally, frequency tables summarizing infection site events will be provided for the SAF.

Injection site event is defined as any AE at the injection site presenting as Injection site erythema, Injection site swelling, Injection site pruritus, or Injection site pain that started on the day of injection.

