In addition, frequency tables will summarize the number of subjects with any event occurring during pre-treatment period.

For the full analysis set the event which occurred during the extension treatment period and during the post treatment follow-up period will be considered.

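### SAE, AESI and preferred-term tables give crude percentages only, so in the full-study window they would understate risk in any arm that stops drug more often

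*SAP*

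**What the plan says.** SAP 6.4.5 defines the adverse event output as frequency tables: "For each AE, the number and percentage of subjects who experienced at least 1 occurrence of the given event will be tabulated". The overall summaries of AEs, SAEs and the two AESI categories are also frequency tables. No person-time denominator is given.

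Two windows apply:
- **Main-period tables** use the treatment-emergent rule of SAP 4.5, which counts events "not later than 30 days after last administration of study intervention".
- **Full-study tables** repeat every AE, SAE and AESI table for "AEs occurred after first intake of study intervention up to 5 months after last intake".

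Treatment length varies by design. Protocol 6.1 states: "Participants will be treated up to 18 months". The synopsis adds "The mandatory extension treatment period is continued until the last study participant has completed its 6 months main treatment period" (or a maximum of 18 months in total), and "The last participant of the whole study will not take part in the extension treatment period". Protocol 1.2 closes observation relative to last dose: "The follow-up period ends 5 months after last study intervention and 4 months after EOMT or EOET". Under Protocol Tables 1–1 and 1–2, a participant who stops early goes directly into follow-up after the early discontinuation visit.

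Other outcomes are handled differently. For both primary safety variables, SAP 6.4.1 gives exposure-adjusted rates per 100 participant-years, Aalen-Johansen estimates with death and premature end of exposure as competing events, and cause-specific hazard ratios. One of those variables is the composite of moderate and severe AEs and SAEs. SAP 6.4.2 repeats this for main plus extension treatment, SAP 6.4.3 for further bleeding outcomes, and SAP 6.2 uses similar methods for efficacy and death events.

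SAP 6.4.5 closes with: "For the full analysis set the event which occurred during the extension treatment period and during the post treatment follow-up period will be considered".

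**The concern.** In the full-study tables, a participant's chance of being counted depends on how long the drug was taken, because the window ends a fixed time after last dose. An arm with more early stopping has less observation time, and so a lower percentage at the same underlying risk. SAP 6.4.1 recognises this for the primary safety variables, but nothing equivalent is planned for SAEs alone, thrombocytopenia, hypersensitivity or any individual preferred term. New safety signals would be read from those tables.

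Unequal stopping is plausible. Under Protocol 7.1, 8.2.2.2 and 8.3.8, bleeding or other AEs, surgery, recurrent thrombocytopenia and hypersensitivity can each lead to permanent discontinuation, and bleeding, thrombocytopenia and hypersensitivity are potential risks listed in Protocol Table 2–1. The documents give no discontinuation rate by arm.

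The last sentence of SAP 6.4.5 is a smaller matter. The full analysis set is everyone randomised (SAP 5), so taken literally it puts never-dosed participants in an adverse event denominator.

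**Working it through.** **Windows.** Doses are 30 days apart, so dose k falls on day 30(k−1) after the first. Tables 1–1 and 1–2 give 6 main-period and 12 extension doses.

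| Doses received | Main-period window, 30(k−1)+30 days | Full-study window, 30(k−1)+150 days |
|---|---|---|
| 1 | 30 (1 month) | 150 (5 months) |
| 6 | 180 (6 months) | 300 (10 months) |
| 18 | not applicable | 660 (22 months) |

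Table 1–2 labels visit 35 approximate month 23, but elapsed time from first dose is 22 months.

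**Reference rate.** The only dropout figure is 15 lost to follow-up per 100 participant-years, across all groups (Protocol 9.2). It gives the planned number of main-period completers: 600 × (1 − 0.15 × 0.5) = 555, as stated; the exponential form gives 600 × exp(−0.075) = 556.6. I use 15 as the reference discontinuation rate, although it is a loss-to-follow-up rate.

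**Model.**
- Discontinuation rate d, constant and independent of the event. The probability of stopping between doses is q = 1 − exp(−d × 30/365.25): 0.0122, 0.0243 and 0.0481 for d = 15, 30 and 60 per 100 participant-years.
- With K planned doses, P(k doses) = (1−q)^(k−1) × q for k < K, and (1−q)^(K−1) for k = K.
- Crude proportion = Σ P(k) × [1 − exp(−λ × window_k)], with λ = 10 per 100 participant-years (the plan's placebo bleeding rate, used as an illustration).
- Main tables: K = 6. Full-study tables: K uniform from 6 to 18.

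The rates of 30 and 60, the uniform spread of planned doses and the constant hazard are assumptions.

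**Equal true hazard in both arms**

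| Table | Discontinuation per 100 PY | Mean observation (years) | Crude % | Ratio to 15 per 100 PY |
|---|---|---|---|---|
| Full-study | 15 | 1.244 | 11.65 | 1.00 |
| Full-study | 30 | 1.182 | 11.09 | 0.95 |
| Full-study | 60 | 1.075 | 10.13 | 0.87 |
| Main | 15 | 0.478 | 4.67 | 1.00 |
| Main | 30 | 0.464 | 4.53 | 0.97 |
| Main | 60 | 0.437 | 4.27 | 0.92 |

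First events divided by time to first event or end of window return the true ratio of 1.00 in every row. For example, in the full-study tables 0.1165/1.165 and 0.1013/1.013 are both 10 per 100 participant-years.

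**Commoner events, full-study.** At 30 and 100 events per 100 participant-years, the ratios are 0.96 and 0.97 for 30 v 15, and 0.88 and 0.91 for 60 v 15.

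**True hazard ratio 1.5, full-study, λ = 10 in the reference arm.** The crude ratio is 16.92/11.65 = 1.45 with equal stopping, 16.12/11.65 = 1.38 at 30 v 15, and 14.75/11.65 = 1.27 at 60 v 15.

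**Events that cluster early.** If the same share of each arm has the event in the first month and nobody does later, the crude ratio is 1.00. The rate ratio is then about 1.244/1.182 = 1.05 at 30 v 15 and 1.244/1.075 = 1.16 at 60 v 15. The error is now in the rate, and in the other direction.

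**The case against.** The strongest reply is that the main safety comparison is already protected. The composite of moderate and severe AEs and SAEs has exposure-adjusted rates and a competing-risk analysis, Protocol 9.4.4 says the safety analyses will be repeated on the full data, and SAP 4.2 shows discontinuation and its reasons by arm, so a reader would see any imbalance. This stands as mitigation. It does not give a rate for SAEs alone, an AESI category or a preferred term, and showing an imbalance does not adjust for it.

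The bias is also modest next to sampling error. At 11.65% with 200 per arm, the 90% half-width for a difference is 1.645 × √(2 × 0.1165 × 0.8835/200) = 5.3 percentage points, against shifts of 0.56 (11.65 − 11.09) and 1.52 (11.65 − 10.13) points. That stands too, in a study described as descriptive. But the shift is systematic and cheap to remove.

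The direction is conditional. An AE that itself causes stopping is already counted, and risk off drug may differ from risk on drug. For early-clustering events the crude percentage is the better summary.

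On the closing sentence of SAP 6.4.5, the SAP also uses full analysis for the study-completion analysis (SAP 4.4), which may be what was meant. Full-study events require a first dose, so never-dosed participants could affect only the denominator.

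**Conclusion.** The point holds as a specific gap. SAEs alone, the two AESI categories and individual preferred terms have only crude percentages, in a window whose length depends on when drug was stopped. If discontinuation differs by arm and the hazard is roughly constant, the percentage understates risk in the arm that stops more. At 10 events per 100 participant-years, the shortfall in the full-study crude ratio is about 5% if discontinuation is 30 v 15 per 100 participant-years and 13% at 60 v 15; in the main-period tables it is 3% and 8%. Both contrasts are assumed.

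A reader might infer more than the documents support:
- **That all adverse event data lack exposure adjustment.** SAP 6.4.1 to 6.4.3 cover the AE/SAE composite and bleeding.
- **That every table spans roughly 5 to 23 months.** Only the full-study tables start at 5 months, and they end at 22; the main-period tables run about 1 to 6.
- **That staggered entry biases the comparison.** Planned length varies with entry date, which randomisation should balance. Only differential stopping biases it.
- **That osocimab will look safer than it is.** No arm-specific discontinuation is given, and with equal discontinuation this bias is nil.

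**What to change.** In SAP 6.4.5, for the full-study tables:
- For SAEs, each AESI category and common preferred terms, add participants with a first event per 100 participant-years of observation. Count time from first dose to first such event or the end of the window. The formula in SAP 6.4.1 divides by time under treatment, which would leave out the post-drug months in which events are counted.
- Apply the existing SAP section 6 rule that incidence rates need at least 3 events in at least one arm.
- Show mean observation time by arm.
- Keep the crude percentages beside the rates, because a constant rate can mislead for events that cluster early.

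In the closing sentence of SAP 6.4.5, replace the full analysis set by the safety analysis set.

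The extension-period denominator should not be restricted to participants who received an extension dose. That selects on tolerance and survival after randomisation, for a table that SAP 6.4.5 does not clearly define.

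The cost is SAP wording and extra columns, from data already collected. The downside is longer tables.

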#### 9.4.1 General Considerations

The statistical analysis will be performed using SAS; the version used will be specified in the statistical analysis plan. In general, all variables including demography and baseline characteristics will be summarized by treatment group and by providing frequency tables for categorical variables and summary statistics for continuous variables.

For the primary analysis, only the main treatment period will be considered. The partial data of a participant's extended treatment period up until primary completion may be presented in separate tables. Furthermore, the primary analysis will be performed on the safety analysis set in accordance with the "population" attribute of the primary estimand.

In general, participants receiving placebo in either the low-dose or the high-dose cohort will be analyzed in a pooled manner. This group will be referred to as placebo group. The group of participants receiving osocimab in the high dose cohort (or low dose cohort) will be referred to as high dose (or low dose osocimab) group.

Where appropriate, the osocimab groups will be additionally displayed in a pooled manner.

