4.1 General Principles

The statistical evaluation will be performed by using the software package SAS release 9.2 or higher (SAS Institute Inc., Cary, NC, USA) or other software if applicable. All variables will be analyzed by descriptive statistical methods. The number of data available and missing data, mean, standard deviation, minimum, quartiles, median, and maximum will be calculated for metric data. Frequency tables will be generated for categorical data.

In general, subjects receiving placebo in either the low dose or the high dose cohort will be analyzed in a pooled manner. This group will be referred to as placebo group. The group of subjects receiving osocimab in the high dose cohort (or low dose cohort) will be referred to as high dose (or low dose) osocimab group.

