4.6 Blind Review

There will be two data assessment lists. The first one will occur after primary completion and the second one will occur after end of study. The results of both data lists will be documented in separate lists of important deviations, validity findings and assignment to analysis set(s). Any changes to the statistical analysis prompted by the results of the review of study data will be documented in an amendment and, if applicable, in a supplement to this SAP.

The results of the final data assessment will be documented in the final list of important deviations, validity findings and assignment to analysis sets. Pharmacodynamic values to be excluded from statistical analysis will be documented in the list of pharmacodynamic values to be flagged as invalid.

5. Analysis Sets

Final decisions regarding the assignment of subjects to analysis sets will be made during the review of study data and documented in the final list of important deviations, validity findings and assignment to analysis set(s) (see section 4.6).

The following populations are defined:

Population	Description
Enrolled	All subjects who sign the ICF
Full Analysis Set	All subjects randomly assigned to study intervention.
Safety Analysis Set	All subjects randomly assigned to study intervention and who took at least 1 dose of study intervention. Subjects will be analyzed according to the intervention they actually received.
Pharmacokinetic analysis set	All osocimab-treated subjects with at least 1 PK sample in accordance with the PK sampling schedule (Section 1.3 and Section 8.5 of the study protocol) and without deviation from the protocol that would interfere with the evaluation of the PK data will be included in the PK analysis.
Pharmacodynamic analysis set	All subjects with at least 1 PD sample in accordance with the PD sampling schedule and without deviation from the protocol that would interfere with the evaluation of the PD data will be included in the PD analysis.
Listing only set	All subjects who signed ICF but are not randomized.

In accordance with the “population” attribute of the primary estimand, the primary analysis set is the safety analysis set.

Supplementary analyses of the efficacy variables will be performed on the full analysis set.

6. Statistical Methodology

In general, the evaluations will be conducted on each osocimab group and on the placebo group.

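### The dedicated injection-site table keeps only same-day reactions and, by default, sets each osocimab dose against a placebo pool of mixed injection volume

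*SAP*

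**What the plan says.** SAP 6.4.5 states that "frequency tables summarizing infection site events will be provided for the SAF". The word infection is a slip for injection, as the definition that follows shows: an event is any AE at the site presenting as "Injection site erythema, Injection site swelling, Injection site pruritus, or Injection site pain that started on the day of injection".

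The other AE tables in that section use the treatment-emergent window, which SAP 4.5 closes "not later than 30 days after last administration of study intervention". They are repeated out to five months after the last dose.

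On the comparator, SAP 4.1 says: "In general, subjects receiving placebo in either the low dose or the high dose cohort will be analyzed in a pooled manner". Protocol 9.4.1 has the same rule. SAP section 6 opens by saying that, in general, "the evaluations will be conducted on each osocimab group and on the placebo group". It then splits placebo into its low-dose and high-dose cohorts for the primary safety and efficacy variables. Injection site events are not named there. SAP 6.4.5 says that the tables by system organ class and preferred term are given by treatment arm, but not whether that means three columns or four. It gives no grouping rule for the injection-site tables.

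Dose is set through injected volume (Protocol 6.1), the solution is 150 mg/mL (Protocol 6.2), and the placebo group is planned as 100 participants at each cohort's volume (Protocol 4.1).

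**The concern.** Tolerability of monthly subcutaneous dosing is part of the primary objective (Protocol section 3), and this table is the only planned summary that combines local reactions into one count. Two features make it harder to read than it needs to be.

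First, the onset rule is much narrower than the treatment-emergent window, and no reason is given. The main-period schedule (Protocol Table 1–1) brings participants back on days 2 and 4 after the loading dose and the first maintenance dose, and on day 4 after each later dose. A reaction that starts the next day can therefore be recorded and then left out of the table meant to describe it.

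Second, placebo volume is matched within each dose cohort, but the default pooling gives up that match. For a local reaction, the amount injected is a possible cause in its own right. A reader judging local tolerability before Phase 3 could then not tell a drug effect from a volume effect.

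**Working it through.** **Where a reaction is counted.** Setting SAP 6.4.5, 4.5 and 6.4.1 side by side for a main-period reaction of one of the four listed kinds:

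- Starts on the injection day: in the dedicated table and in the preferred-term tables.
- Starts later, mild: in the preferred-term tables only.
- Starts later, moderate, severe or serious: in the preferred-term tables, and it can count towards the second primary endpoint, but not in the dedicated table.

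The loss is thus confined to the combined summary. Its size depends on the share *f* of reactions with later onset, which the documents do not give. With an assumed true risk of 10%, the table would show 10% × (1 − *f*): 9%, 7% and 5% for assumed *f* of 0.1, 0.3 and 0.5.

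**Volumes (dose ÷ 150 mg/mL).**

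- High-dose cohort: 210/150 = 1.4 mL loading, 105/150 = 0.7 mL maintenance.
- Low-dose cohort: 105/150 = 0.7 mL loading, 52.5/150 = 0.35 mL maintenance.

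The high-dose volume is twice the low-dose volume at every administration.

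**Composition of the pool.** With 600 randomized 2:1:2:1 (SAP 3.1), each placebo arm has 600 × 1/6 = 100 and each osocimab arm 600 × 2/6 = 200. This reproduces the plan's 200 placebo participants as 100 + 100. The mean volume in the pool is (1.4 + 0.7)/2 = 1.05 mL loading and (0.7 + 0.35)/2 = 0.525 mL maintenance. For each osocimab arm, half of the pool matches its volume and half does not.

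**What pooling would do with no drug effect.** Let the reaction risk be *a* at low volume and *b* at high volume. The pool then shows (*a* + *b*)/2, the low dose appears to differ from it by (*a* − *b*)/2, and the high dose by (*b* − *a*)/2. All risks below are assumptions.

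- *a* = 2%, *b* = 4%: pool 3%; low dose −1 point (ratio 0.67), high dose +1 point (ratio 1.33).
- *a* = 5%, *b* = 10%: pool 7.5%; low dose −2.5 points, high dose +2.5 points (ratios again 0.67 and 1.33).
- *a* = *b* = 5%: pool 5%; no distortion.

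**Price of matching.** A matched contrast is 200 versus 100 instead of 200 versus 200. With equal variances the standard error of a risk difference changes by √[(1/200 + 1/100)/(1/200 + 1/200)] = √(0.015/0.010) = 1.22.

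**The case against.** The strongest reply is that little is lost. The table is an addition to a full set of AE tables that count later-onset reactions term by term. No test or interval is planned for it, all analyses are descriptive (Protocol 9.1), and injection site events are not a listed endpoint. All of this stands, and it is why the point is minor. It does not supply a combined count that includes later onset: the preferred-term tables list single terms, and a participant with two terms cannot be counted once from them.

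A second reply is that four columns may already be intended. Protocol 1.1 speaks of 3 groups and 4 arms, and SAP 9.2 calls the four randomized arms treatment arms. This stands as an ambiguity. A reader might infer that pooled placebo is prescribed for this table; the documents state it only as the general rule.

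Three further inferences go beyond the text:

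- That the trial will miss delayed local reactions. They remain in the general AE tables, and the share with later onset is unknown.
- That the calendar-day rule biases the comparison, because "Osocimab/ placebo is administered within one hour (60 minutes) prior to start of dialysis session" and later sessions leave fewer hours in the day. No session times are given and nothing links them to treatment, so a shorter window would be expected to affect the arms alike.
- That pooling makes the low dose look better and the high dose worse. This requires reactions to rise with volume, which the documents do not say, and half of the pool is matched in any case.

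**Conclusion.** The point holds as a limitation of one descriptive table. By definition, that table excludes reactions starting after the injection day. Under the general rule, its comparator is an even mix of two volumes, so that half of it differs in volume from each osocimab arm. Whether this distorts anything depends on an assumption that volume affects local reactions. The distortion is zero if it does not, and under the assumed risks above it is 1 to 2.5 percentage points in either direction. The documents give no injection-site rates, so the actual size cannot be stated. Neither primary endpoint definition is affected, and no key result is in error. The change is worth making because it costs almost nothing.

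**What to change.** In SAP 6.4.5:

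- Keep the four listed presentations, but count events of any treatment-emergent onset, with same-day onset as a subset row.
- Show low-volume and high-volume placebo as separate columns beside the pooled column, so that each osocimab group can be read against its own cohort's placebo.
- Correct 'infection site' to 'injection site'.

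The cost is one definition and one table layout; AE onset dates and randomized arm are already recorded. The matched contrasts are less precise (about 200 versus 100, standard error about 1.22 times larger), but the pooled column stays for readers who prefer it. SAP 6.5 says that the primary analysis is already complete, so the new rows and columns should be labelled as supplementary in the final analysis.
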